7. INTERIM ANALYSES

7.1. Introduction

No formal interim analysis will be conducted for this study. As this is an open-label study, the sponsor may conduct unblinded reviews of the data during the course of the study for the purpose of safety assessment and/or supporting clinical development.

7.2. Interim Analyses and Summaries

Not applicable

9. APPENDICES

Appendix 1. Summary of Efficacy Analyses

The table below summarizes analyses of efficacy endpoints. The efficacy evaluable set with adherence to protocol regimen will be used for all efficacy analyses.

Endpoint	Cohort	Analysis Type	Analysis Model
Primary			
Change from baseline to Month 12 in lean body mass (%) measured by DEXA	Adult	Main analysis	MMRM
		Sensitivity/supplementary analysis	N/A (Summary statistics)
	GH naïve pediatric and GH treated pediatric	Main analysis	N/A (Summary statistics)
Secondary			
Change from baseline to Month 12 in lean body mass (%) measured by BIA	Adult	Main analysis	MMRM
		Sensitivity/supplementary analysis	N/A (Summary statistics)
	GH naïve pediatric and GH treated pediatric	Main analysis	N/A (Summary statistics)
Change from baseline to Month 12 in body fat (%) measured by DEXA	Adult	Main analysis	MMRM
		Sensitivity/supplementary analysis	N/A (Summary statistics)
	GH naïve pediatric and GH treated pediatric	Main analysis	N/A (Summary statistics)
Change from baseline to Month 12 in adipose tissue distribution measured by abdominal CT	Adult, GH naïve pediatric, and GH treated pediatric	Main analysis	N/A (Summary statistics)
Change from baseline to Month 6 in lean body mass (%) measured by DEXA	Adult	Main analysis	MMRM
		Sensitivity/supplementary analysis	N/A (Summary statistics)
CCI			

CCI

This figure displays a 7x4 grid of black bars, representing data for 7 categories (rows) across 4 conditions (columns). The bars are of varying lengths, indicating the magnitude of the data for each category and condition. The first bar in the top row is labeled 'CCI' in red at the top.

Category	Condition 1	Condition 2	Condition 3	Condition 4
1	Short	Medium	Very Short	Medium
2	Medium	Medium	Short	Medium
3	Medium	Medium	Short	Medium
4	Medium	Medium	Short	Medium
5	Medium	Medium	Short	Medium
6	Medium	Medium	Medium	Medium
7	Medium	Medium	Medium	Medium

Appendix 2. Definition and Use of Visit Windows in Reporting

The following visit windows will be used for summary analyses by visit labels.

Visit Label	Target Day	Definition [Day window]
Screening		Days -28 to -1
Day 1	1	Baseline
Month 1	28	Days 14 to 41
Month 2	56	Days 42 to 69
Month 3	84	Days 70 to 97
Month 6	182	Days 137 to 227
Month 9	273	Days 228 to 318
Month 12	364	Days 319 to 409

If two or more visits fall into the same window, keep the one closest to the Target Day. If two visits are equally distant from the Target Day in absolute value, the later visit should be used.

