1.3. Schedule of Activities

The SoA table provides an overview of the protocol visits and procedures. Refer to the **STUDY ASSESSMENTS AND PROCEDURES** section of the protocol for detailed information on each procedure and assessment required for compliance with the protocol.

The investigator may schedule visits (unplanned visits) in addition to those listed in the SoA table, in order to conduct evaluations or assessments required to protect the well-being of the participant.

	Screening Period	Treatment Period								Extension Period ^l	End of Study	Follow-up
Visit Identifier^a Abbreviations used in this table may be found in Appendix 11	Screening	Day 1 ^b	Month 1 Week 4	Month 2 ^b Week 8	Month 3 Week 12	Month 6 Week 26	Month 9 Week 39	Month 12 Week 52	Month 18/24/30/36/42 Week 78/104/130/156/182	End of Study/Early Termination/Discontinuation	28 days after EOS visit ^k	
Visit Window	Day -28 to -1	N/A	±3d	±3d	±3d	±3d	±7d	±7d	±14d			+7d
Informed consent/assent	X											
Registration	X											
Inclusion/exclusion criteria	X	X										
Medical history	X	X										
Demographics	X	X										
Physical examination, including behavioral and mental health status	X	X										
Vital signs	X	X	X	X ^b	X	X	X	X	X	X		
Diet/exercise management compliance check	X	X	X		X	X	X	X	X			
Weight, BMI	X	X	X		X	X	X	X	X ^m	X		
Height ⁱ	X	X ^c	X ^c		X ^c	X ^c	X ^c	X	X ^{c, m}	X		
Bone age ^c		X						X		X ^d		
Assessment of childbearing potential	X											
Pregnancy testing (WOCBP only)	X					X		X	X	X		

PFIZER CONFIDENTIAL

	Screening Period	Treatment Period								Extension Period ^l	End of Study	Follow-up
		Day 1 ^h	Month 1 Week 4	Month 2 ^b Week 8	Month 3 Week 12	Month 6 Week 26	Month 9 Week 39	Month 12 Week 52	Month 18/24/30/36/42 Week 78/104/130/156/182			
Visit Identifier^a Abbreviations used in this table may be found in Appendix 11	Screening											
Visit Window	Day -28 to -1	N/A	±3d	±3d	±3d	±3d	±7d	±7d	±14d			+7d
Contraception check (WOCBP only)		X	X		X	X	X	X	X	X	X	X
Study intervention												
Dispense study intervention		X	X		X	X	X	X	X ^f			
Review injection diary			X		X	X	X	X	X		X	
Assessments												
Efficacy												
Body composition (DEXA) ^j		X				X ^e		X		X ^d		
Abdominal CT ^j		X						X		X ^d		
Body composition (BIA)		X	X		X	X	X	X	X ^m	X		
Waist circumference		X						X		X ^d		
Safety												
Concomitant treatment(s)		X	→	→	→	→	→	→	→	→	X	
Serious and nonserious adverse event monitoring	X	→	→	→	→	→	→	→	→	→	X	
Laboratory ^g												

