Blood count	X	X			X	X		X	X	X		
Blood chemistry	X	X			X	X		X	X	X		
IGF-1, IGF-1 SDS	X	X	X		X	X		X	X	X		
Thyroid function (TSH, FT4)	X	X	X		X	X		X	X	X		
Cortisol	X	X	X		X	X		X	X	X		
Gonadal function (LH, FSH, E2, testosterone)	X	X				X		X	X	X		
HbA1c	X	X	X	X ^b	X	X	X	X	X	X	X	
Casual blood glucose		X ^b	X ^b	X ^b	X ^b	X ^b	X ^b	X ^b	X ^b	X ^b	X ^b	
Lipid profile	X	X			X	X		X	X	X	X	

PFIZER CONFIDENTIAL

	Screening Period	Treatment Period								Extension Period ^l	End of Study	Follow-up
		Day 1 ^h	Month 1 Week 4	Month 2 ^b Week 8	Month 3 Week 12	Month 6 Week 26	Month 9 Week 39	Month 12 Week 52	Month 18/24/30/36/42 Week 78/104/130/156/182			
Visit Identifier^a Abbreviations used in this table may be found in Appendix 11	Screening									End of Study/Early Termination/Discontinuation	28 days after EOS visit ^k	
Visit Window	Day -28 to -1	N/A	±3d	±3d	±3d	±3d	±7d	±7d	±14d			+7d

a. Day relative to start of study intervention (Day 1).
b. Applicable only for participants with diabetes.
c. For pediatric cohorts only. If the participant reaches bone age of 17 for boys and 15 for girls, the assessment is not necessary after that.
d. Applicable only for early termination before Month 12.
e. For adult cohort only.
f. For extension period, study intervention can be dispensed every 3 months in case a participant cannot bring home a 6-month drug supply at once. If a participant chooses to receive drug supply every 3 months, safety assessment (at least but not limited to: AE/SAE, concomitant treatment) should be confirmed via physical site visit or telehealth before dispensing for the remaining 3 months. If a participant choose a 6-month drug supply, he/she will come back to the site for next protocol specified visits and complete assessments according to protocol.
g. All laboratory testing can be performed locally at the site. Fasting is not required for any of lab tests in this study.
h. Laboratory test result at Screening can be used for Day 1 if the test was performed within 7 days before Day 1 visit.
i. Height measurement at Screening can be used for Day 1 if the measurement was performed within 14 days before Day 1 visit.
j. DEXA/Abdominal CT scan prior to Day 1 visit is acceptable if the evaluation was performed within 7 days before Day 1 visit.
k. Follow-up visit may become telephone visit at investigator's discretion.

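### Do the SAP's visit windows leave an accepted pre-Day 1 scan without baseline status, and Days 98–136 wrongly without a label?

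*SAP*

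**What the plan says.** SAP Appendix 2 introduces its table with "The following visit windows will be used for summary analyses by visit labels". Screening covers Days -28 to -1. The Day 1 row has target day 1 and is defined only as Baseline. Month 3 (target 84) covers Days 70–97, and Month 6 (target 182) is "Days 137 to 227". The selection rule begins: "If two or more visits fall into the same window, keep the one closest to the Target Day".

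The footnotes to Protocol 1.3 (Schedule of Activities) accept some earlier values:
- Scans (footnote j): "DEXA/Abdominal CT scan prior to Day 1 visit is acceptable if the evaluation was performed within 7 days before Day 1 visit".
- Laboratory tests (footnote h): "Laboratory test result at Screening can be used for Day 1 if the test was performed within 7 days before Day 1 visit".
- Height (footnote i): "Height measurement at Screening can be used for Day 1 if the measurement was performed within 14 days before Day 1 visit".

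Day 1 height carries footnote c, "For pediatric cohorts only", so adults have their scheduled pre-treatment height at Screening only. The same section says: "The investigator may schedule visits (unplanned visits) in addition to those listed in the SoA table".

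SAP section 6 requires a baseline and at least one later value for any change analysis, and SAP 5.3 rules out imputation. SAP 3.4 lists height among the baseline variables, and SAP 6.6.3 summarises its change from baseline under the sponsor's reporting standards (CaPS), which are not among the documents.

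**The concern.** Three things look wrong when the table is read alone.

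- **Baseline.** A DEXA scan on Day -3 complies with the protocol but falls in the range labelled Screening. If a program took the label literally, that participant would have no baseline and would drop out of the change analysis. The DEXA baseline matters twice in adults: it enters the primary change score and it is a covariate in the MMRM. One participant is 1/20 = 5% of the planned adult cohort, or 1/5 = 20% of a pediatric cohort. Adult height looks worse still, because no Day 1 value is scheduled.
- **Gap.** The windows run without a break over Days 14–97 and 137–409, but Days 98–136 belong to no visit. A late Month 3 BIA or laboratory result could vanish from the by-visit summaries, and BIA feeds the key secondary MMRM.
- **Selection rule.** It keeps the closest visit, not the closest non-missing value. An unplanned visit without the measurement could, read literally, displace a valid result.

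**Working it through.** **1. Reproduce the table.** Target day = 7 × protocol week. Offsets are the window limits minus the target. Tolerances are from Protocol 1.3.

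| Visit | Target | SAP window | Offsets | Days within protocol tolerance |
|---|---|---|---|---|
| Month 1 | 7×4 = 28 | 14–41 | -14/+13 | 25–31 |
| Month 2 | 7×8 = 56 | 42–69 | -14/+13 | 53–59 |
| Month 3 | 7×12 = 84 | 70–97 | -14/+13 | 81–87 |
| Month 6 | 7×26 = 182 | 137–227 | -45/+45 | 179–185 |
| Month 9 | 7×39 = 273 | 228–318 | -45/+45 | 266–280 |
| Month 12 | 7×52 = 364 | 319–409 | -45/+45 | 357–371 |

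All twelve limits fit two fixed rules. No windows overlap, and every within-tolerance visit falls in its own window.

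**2. Where the gap comes from.** The early windows are 14 + 13 + 1 = 28 days wide, equal to the 28-day spacing of their targets. The later ones are 45 + 45 + 1 = 91 days wide, equal to their 91-day spacing. Between Months 3 and 6 the spacing is 182 − 84 = 98 days, so 98 − 13 − 45 − 1 = 39 days remain: Days 98–136. Days 2–13 (12 days) are also unlabelled, and nothing is scheduled there.

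**3. What can land in it.**
- A Month 3 visit must be at least 98 − 84 = 14 days late, which is 98 − 87 = 11 days beyond tolerance.
- A Month 6 visit must be at least 182 − 136 = 46 days early, which is 179 − 136 = 43 days beyond tolerance.
- During treatment DEXA is scheduled only at Month 6 (adults) and Month 12, so no Month 3 scan exists to be lost. An early-termination scan falls under the exclusion of data after discontinuation in SAP 6.1.1.1.

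**4. Would closing the gap be better?** Splitting at the midpoint, (84 + 182)/2 = 133, gives Month 3 = Days 70–132 and Month 6 = Days 133–227. Month 3 would then run from -14 to 132 − 84 = +48 days, so a BIA taken 48 days late would count as Month 3. For DEXA, only Days 133–136 would gain a usable label (Month 6), for a scan 46 to 49 days early.

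**5. Baseline, side by side.** In the Schedule of Activities the only pre-treatment entry for DEXA and CT is Day 1, and footnote j qualifies that entry. A scan on Day -5 is therefore the Day 1 scan, with no separate Screening scan to compete with it. Footnotes h and i state outright that the earlier result may stand for Day 1. In Appendix 2 the Day 1 row alone is defined by a concept rather than a day range, which leaves room for these allowances.

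**6. Adult height.** Footnote i concerns reuse of a Screening height at Day 1. Adults have no Day 1 height, so its 14-day limit does not restrict theirs. BMI is scheduled at Day 1 for everyone, so the adult Screening height must already serve.

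**7. Size if a baseline were dropped.** The 95% CI half-width for a mean, in SD units, is t(0.975, n−1)/√n.
- n = 20 to 19: 0.468 to 0.482 (+3%).
- n = 5 to 4: 1.242 to 1.591 (+28%).

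These figures apply only if someone discards the single pre-treatment scan that the protocol accepts.

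**The case for a change.** The best case for a change is that the primary baseline should not rest on inference. SAP version 2 recalculated Appendix 2 to follow the protocol amendment. That same amendment clarified the 7-day allowance for DEXA, yet the allowance was not carried into the SAP. The study is open label and the sponsor may review data while it runs, so pre-specification has value, and a sentence of text costs almost nothing. Late visits are also plausible: Protocol 10.10.6 confines efficacy assessments to on-site visits during public emergencies. Finally, the four other boundaries between successive monthly windows coincide with midpoints of adjacent targets (42, 70, 227.5, 318.5), so the Month 3/Month 6 boundary looks like an oversight.

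What stands is that the readable SAP has no explicit definition of the baseline record. The rest is weaker.
- The midpoint pattern appears only where targets are equally spaced, and there fixed offsets give the same limits. A midpoint rule does not explain the start of Month 1: the midpoint of Days 1 and 28 is 14.5, but the window opens at 14. Nor does it explain the end of Month 12: the next visit is Week 78 = Day 546, the midpoint is (364 + 546)/2 = 455, and the window closes at 409.
- Leaving a BIA value unlabelled when it is at least 14 days late is a defensible choice. That participant's other visits still enter the BIA model.
- The selection rule is ordinarily applied to records that hold the measurement. Protocol 1.3 describes unplanned visits as serving the participant's well-being, and no scheduled measure is shown to be displaced.

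**Conclusion.** No change follows. The baseline and selection-rule points are missing detail that an analyst holding both documents would fill in one sensible way: take the accepted pre-treatment value, or the adult Screening height, as baseline, and choose among records that contain the measure. The 39 unlabelled days result from a consistent fixed-offset table. They catch no visit held within tolerance and no DEXA scan done on schedule, and closing them at the midpoint would trade the gap for a Month 3 window of -14/+48 days. Reasonable statisticians would differ on that choice.

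No stated rule is shown to give a wrong primary result. The 5% and 20% losses, and the wider intervals shown above, need an implausible programming decision. The conclusion assumes that programmers read Appendix 2 together with the schedule footnotes, and that CaPS and the redacted text contain nothing to the contrary; neither could be checked. The documents do not say how many assessments were early, late or unplanned.

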8.2.3. Clinical Safety Laboratory Assessments

See [Appendix 2](#) for the list of clinical safety laboratory tests to be performed and the [SoA](#) for the timing and frequency. All protocol-required laboratory assessments, as defined in [Appendix 2](#), must be conducted in accordance with the laboratory manual and the [SoA](#). Unscheduled clinical laboratory measurements may be obtained at any time during the study to assess any perceived safety issues.

For participants with preexisting diabetes, casual blood glucose tests are to be performed in addition to HbA1c at the specified visits to make sure the participants' blood glucose level is maintained within acceptable range. Last mealtime before blood draw should be recorded along with the casual glucose tests.

The investigator must review the laboratory report, document this review, and record any clinically relevant changes occurring during the study in the AE section of the CRF. Clinically significant abnormal laboratory findings are those which are not associated with the underlying disease, unless judged by the investigator to be more severe than expected for the participant's condition.

All laboratory tests with values considered clinically significantly abnormal during participation in the study or within 28 days after the last dose of study intervention should be repeated until the values return to normal or baseline or are no longer considered clinically significant by the investigator or medical monitor.

If such values do not return to normal/baseline within a period of time judged reasonable by the investigator, the etiology should be identified and the sponsor notified.

See [Appendix 6](#) for suggested actions and follow-up assessments in the event of potential drug-induced liver injury.

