1. VERSION HISTORY

Table 1. Summary of Changes

Version/ Date	Associated Protocol Amendment	Rationale	Specific Changes
3 16 Dec 2022	Amendment 1 13 Dec 2021	Some summaries were added.	
6.6.1. Adverse Events
 
Added the summaries for TEAEs of special interest.
 
Overall: Minor edits for the description maintenance.

2 13 May 2022	Amendment 1 13 Dec 2021	Some clarifications were added.	
Sections 3: Added the calculation expressions.
 
Section 3.5.2: Added the table footer according to the protocol amendment.
 
Section 4: Updated to the accurate description.
 
Sections 6.5.3: Added the analysis for medication errors.
 
Appendix 2: Applied the visit windows to safety analyses and re-calculated the target days and the day windows to weekly basis according to the protocol amendment.
 
Overall: Minor edits for the description maintenance.

1 21 Oct 2020	Original 21 Aug 2020	N/A	N/A

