6.6.2. Laboratory Data

Laboratory data will be summarized in accordance with CaPS.

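### In by-visit laboratory summaries, SAP Appendix 2 lets a repeat test replace the abnormal scheduled result that triggered it, when that sample was taken early

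*SAP*

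**What the plan says.** SAP Appendix 2 opens with its scope: "The following visit windows will be used for summary analyses by visit labels". Its selection rule is "If two or more visits fall into the same window, keep the one closest to the Target Day", followed by the tie rule "If two visits are equally distant from the Target Day in absolute value, the later visit should be used". Neither sentence separates scheduled from unscheduled visits. The windows are wide: Month 12 has target Day 364 and runs "Days 319 to 409", 45 days either side. The SAP version history records for version 2: "Appendix 2: Applied the visit windows to safety analyses".

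SAP 6.6.2 does not add a rule for repeats or worst values. It says "Laboratory data will be summarized in accordance with CaPS", which refers to the sponsor's reporting standard.

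Protocol 8.2.3 says that clinically significantly abnormal laboratory results "should be repeated until the values return to normal or baseline or are no longer considered clinically significant". Protocol 8.2 and 8.2.3 also allow unscheduled laboratory tests at any time for a perceived safety issue. The introduction to the Schedule of Activities (Protocol 1.3) calls extra contacts unplanned visits, so they count as visits under the wording of Appendix 2.

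**The concern.** The result and its repeat usually fall in the same SAP window, and only one of them can represent the visit. A mandatory repeat exists because the first value was abnormal, and the series stops once the value has improved or no longer matters clinically. A rule that can pick the repeat therefore makes selection depend partly on the outcome, and the by-visit summary tends to look closer to normal than the scheduled sample did.

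Clinical laboratory values are a listed safety endpoint. Each pediatric cohort has about 5 participants, so one value carries a weight of 1/5 in a by-visit mean, against 1/20 in the adult cohort. A single substitution can be visible in a pediatric table.

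**Working it through.** **Inputs from the documents**
- Selection and tie rules, Target Days and windows: SAP Appendix 2.
- Protocol visit windows: ±3 days for Months 1, 2, 3 and 6; ±7 days for Months 9 and 12 (Schedule of Activities).
- Repeat requirement: Protocol 8.2.3.

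**Assumptions**
- The lag L between the scheduled sample and the repeat. Protocol 8.2.3 gives none. The nearest figure is in Protocol Appendix 6: for potential Hy's law cases, return is preferred within 48 hours of awareness of the result. That makes short lags plausible for one type of case only.
- Each day of the protocol window is equally likely for the scheduled visit.

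**Condition for replacement.** Let the scheduled sample fall at offset o from the Target Day and the repeat L days later. The repeat is kept when |o + L| ≤ |o|. This requires o < 0 and, with k = |o| days early, L ≤ 2k. The case L = 2k is the tie. If the scheduled sample is on or after the Target Day, it is always kept over a later repeat.

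**Examples**
- Month 6, Target Day 182, abnormal result on Day 179 (k = 3): a repeat on Days 180 to 185 replaces it, Day 185 through the tie rule. A repeat on Day 186 does not.
- Month 12, Target Day 364, abnormal result on Day 357 (k = 7): a repeat on Days 358 to 371 replaces it, Day 371 through the tie rule. A repeat on Day 372 does not.

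**Share of visit days on which the repeat replaces the result.** With a protocol window of ±w days there are 2w + 1 possible days. When they are centred on the Target Day, the early days with k ≥ L/2 number w − ⌈L/2⌉ + 1 (zero if negative). For w = 3 and L = 2 this is 3 − 1 + 1 = 3, giving 3/7. For w = 7 and L = 2 it is 7 − 1 + 1 = 7, giving 7/15.

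The centring is itself uncertain. If Week 26 means 26 × 7 = 182 days after Day 1, the nominal visit is Day 183, one day after the SAP Target Day. One early day is then lost and the count is w − ⌈L/2⌉.

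| Assumed lag L | ±3 days, centred | ±3 days, nominal visit one day later | ±7 days, centred | ±7 days, nominal visit one day later |
|---|---|---|---|---|
| 2 days | 3/7 (43%) | 2/7 (29%) | 7/15 (47%) | 6/15 (40%) |
| 4 days | 2/7 (29%) | 1/7 (14%) | 6/15 (40%) | 5/15 (33%) |
| 6 days | 1/7 (14%) | 0 | 5/15 (33%) | 4/15 (27%) |
| 7 days | 0 | 0 | 4/15 (27%) | 3/15 (20%) |
| 14 days | 0 | 0 | 1/15 (7%) | 0 |

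**Role of the tie rule.** At L = 2 and ±3 days centred, the offsets −3 and −2 are replaced through closeness and −1 through the tie. Without the tie rule the share is 2/7 instead of 3/7. Closeness to target does most of the work.

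**Which tests are affected.** Blood count, chemistry and lipids are drawn at Months 3, 6 and 12, so the ±7-day columns matter for them only at Month 12. At Month 9 only HbA1c is drawn, plus casual glucose in participants with diabetes.

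**After the fix.** If the scheduled result takes priority whenever it exists, every cell in the table becomes 0.

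**The case against.** The case against has several parts.

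- **Consequence is limited.** The study is descriptive, without hypothesis tests, and no stated decision rests on by-visit laboratory means. Clinically relevant laboratory changes go into the adverse event record (Protocol 8.2.3). Protocol 10.3.1 makes an abnormal result that needs further diagnostic testing an adverse event, which a required repeat arguably meets. Listings are produced on the full analysis set. All of this stands: the triggering result is not lost from the report. It does not correct the by-visit table.
- **The sponsor standard may already deal with it.** SAP 6.6.2 defers to a standard that is not among the documents and may prioritise scheduled or worst values. That is possible, but Appendix 2 is the rule the SAP states, and it contains no such priority.
- **The rule is prespecified and does not look at the values.** True of the rule itself. The existence and stopping of mandatory repeats do depend on the values.
- **The direction is not fixed.** A reader might infer that substitution always moves summaries toward normal, or that the winner of a tie is always the repeat. The documents do not support either. A repeat may still be abnormal, since the series may end with a value merely no longer clinically significant, and an early repeat may not have improved. An unscheduled test prompted by a safety concern can displace a normal scheduled value, and a scheduled visit can win a tie against an earlier unscheduled one.
- **The reach is narrower than all safety data.** A reader might extend the point to vital signs. Protocol 8.2.3 mandates repeats for laboratory values only, and only for those judged clinically significantly abnormal.

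**Conclusion.** The point holds for by-visit laboratory summaries. On the text as written, a repeat within 2k days replaces a scheduled abnormal value taken k days early, and no visible rule prevents it. At an assumed 2-day lag the share of visit days affected is 2/7 to 3/7 for ±3-day visits and 6/15 to 7/15 for ±7-day visits. It falls to 0 for ±3-day visits from a 7-day lag. In every case enumerated the scheduled value is kept more often than it is replaced.

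These are conditional shares, resting on visits inside the protocol window, equally likely visit days and an assumed lag. SAP windows also accept visits outside the protocol window, where the exposure is larger: a sample 10 days early could be replaced by a repeat up to 20 days later. The documents give no frequency of clinically significant abnormalities, so neither an overall rate nor a shift in a cohort mean can be calculated.

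A reader might infer that the plan conceals laboratory safety signals. It does not: adverse event records and listings retain them. The defect is an avoidable, outcome-related distortion of one set of tables, worth correcting because the correction is cheap.

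**What to change.** In SAP Appendix 2, state that for by-visit laboratory summaries the scheduled result takes priority for its label, and that an unscheduled result in the window is used only if the scheduled one is missing. The closest-day and tie rules then apply only among what remains.

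In SAP 6.6.2, state that any laboratory abnormality table uses all post-baseline results, unscheduled ones included. If the sponsor standard already does either of these, a sentence saying so is enough.

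The cost is SAP wording and minor programming, with no new data. Laboratory summaries may look slightly less favourable.
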